### **7.6.3. Follow-up of Incidents**

#### **Follow-up of Incidents:**

During the study:

- All incidents will be followed until resolution of the event, until the condition stabilizes, until the condition is otherwise explained, or until the subject is lost to follow-up. This applies to all subjects, including those withdrawn prematurely. The investigator is responsible for ensuring that follow-up includes any supplemental investigations as may be indicated to elucidate as completely as practical the nature of the incident.
- New or updated information will be recorded on the originally completed form with all changes signed and dated by the investigator.

After the study:

- Investigators are not obligated to actively seek reports of incidents in former subjects. However, if the investigator learns of any incident at any time after a subject has been discharged from the study, and such incident is reasonably related to a GSKCH medical device provided for the study, the investigator will promptly notify GSKCH.

#### **Regulatory and Ethics Reporting Requirements for Incidents:**

- The investigator will promptly report all incidents occurring with any GSKCH medical device provided for use in the study within 24 hours. GSKCH has a legal responsibility to notify appropriate regulatory bodies and other entities about certain safety information relating to medical devices being used in

 GlaxoSmithKline	Document Name	Clinical Protocol 204930		
	Type	Version	Document Identifier	Effective Date
	eldo_clinical_doc	6.0; Most-Recent; Effective; CURRENT	090032d580c189ed	12-Sep-2016 05:12:55
	Reason For Issue	Auto Issue		

clinical studies. Prompt notification of incidents by the investigator to GSKCH is essential in order to meet legal obligations and ethical responsibility towards the safety of subjects.

- The investigator, or responsible person according to local requirements, will comply with the applicable local regulatory requirements relating to the reporting of incidents to the IEC.

## 7.7. Collection of Pregnancy Information

### 7.7.1. Time Period for Collecting of Pregnancy Information

#### Collection of Pregnancy Information:

- Pregnancy information will be collected on all pregnancies reported following administration of any investigational product. Information on pregnancy identified during the screening phase and prior to investigational product administration does not need to be collected.

### 7.7.2. Action to be Taken if Pregnancy Occurs

#### Action to be Taken:

- The investigator will collect pregnancy information on any subject who becomes pregnant while participating in the study after administration of the investigational product. The investigator will record pregnancy information on the appropriate form and submit it to GSKCH within 2 weeks of learning of the subject becoming pregnant. The subject will be followed to determine the outcome of the pregnancy. Information on the status of the mother and infant / neonate (including concomitant medications taken by the mother during the pregnancy) will be forwarded to GSKCH. Generally, follow-up will be no longer than 6 to 8 weeks following the estimated delivery date. Any termination of the pregnancy will be reported.
- While pregnancy itself is not considered to be an AE, any pregnancy complication or elective termination for medical reasons will be recorded as an AE or SAE.
- A spontaneous abortion is always considered to be an SAE and will be reported as such. An SAE occurring in association with a pregnancy, brought to the investigator's attention after the subject completed the study and considered by the investigator as possibly related to the investigational product, must be promptly forwarded to GSK.
- While the investigator is not obliged to actively seek this information in former study participants, he or she may learn of an SAE through spontaneous

 GlaxoSmithKline	Document Name	Clinical Protocol 204930		
	Type	Version	Document Identifier	Effective Date
	eldo_clinical_doc	6.0; Most-Recent; Effective; CURRENT	090032d580c189ed	12-Sep-2016 05:12:55
	Reason For Issue	Auto Issue		

reporting.

- For non-medicinal or licensed products with no pregnancy warning on the label, use the following text: “There is no requirement for the subject to be withdrawn from the study as a result of the pregnancy. However if they are withdrawn, this should be recorded in the appropriate section of the CRF.”

## 8. DATA MANAGEMENT

For this study subject data will be entered into an electronic case report form, using a GSKCH validated data system.

### 8.1. Source Documents/ Data

The source documents (e.g. hospital records, clinical and office charts, laboratory notes, memoranda, subjects’ diaries or evaluation checklists, pharmacy dispensing records, recorded data from automated instruments, microfiches, photographic negatives, microfilm or magnetic media, x-rays, subject files and records kept at the pharmacy, at the laboratory and at the medico-technical departments involved in the clinical study) which contain the source of data recorded in the CRF should be specified in the Source Document Designation Form. In some cases the CRF can be used as a source document.

Each subject will be assigned and identified by a unique Screening Number. Any reference made to an individual subject within the study must be done using the unique Screening Number.

### 8.2. Electronic Case Report Form

A CRF is a printed, optical, or electronic document designed to record all of the protocol required information to be reported to the sponsor on each trial subject.

For each subject who has given informed consent/assent and has been screened, CRF must be completed and signed by the Principal Investigator (or authorized designee) to certify that the data are complete and correct.

Management of clinical data will be performed in accordance with applicable GSKCH standards and data cleaning procedures to ensure the integrity of the data e.g. removing errors and inconsistencies in the data.

 GlaxoSmithKline	Document Name	Clinical Protocol 204930		
	Type	Version	Document Identifier	Effective Date
	eldo_clinical_doc	6.0; Most-Recent; Effective; CURRENT	090032d580c189ed	12-Sep-2016 05:12:55
	Reason For Issue	Auto Issue		

In order to protect the privacy of subjects, no Personally Identifiable Information (PII) (including the subject's name or initials or birth date) is to be recorded in the CRF or as part of the query text.

Adverse events and concomitant medications terms (if applicable) will be coded using MedDRA (Medical Dictionary for Regulatory Activities) and an internal validated medication dictionary, GSKDrug.

Subject data will be entered into GSKCH defined CRFs and transmitted electronically to GSKCH in a validated (21 CFR Part 11 compliant) web-based electronic data capture system (InForm™).

All CRF pages should be completed during a subject assessment when the CRF has been designated as the source. Data that is sourced elsewhere should be entered into the CRF in an agreed upon timeframe between the Investigator and Sponsor.

The CRFs (including queries, query responses and audit trails) will be retained by GSKCH. Site data archived compact discs (CD(s)) prepared by a third party will be sent to the investigator to maintain as the investigator copy following the decommissioning of the study.

### 8.3. Data Handling

Documentation of all data management activities should allow step-by-step retrospective assessment of data quality and study performance. Any changes or corrections to data will be performed in the Electronic Data Capture (EDC) System, and it will include rationale for changes. The EDC system has an audit trail, which will provide a complete record of the changes and corrections endorsed by the Investigator.

#### 8.3.1. Data Queries

Programmed edit checks will be generated automatically, as the data is being entered into the system. Data Management will also run reports and listings on the CRF data, in addition to the queries already programmed and generated by the system, to raise manual queries as needed for site clarification or correction. The Clinical Dictionary Development and Management Group will raise queries as needed on safety data to code the terms (Adverse Events and Drugs) are reported appropriately.

The study monitor at the study site will review the CRFs in accordance with the monitoring plan, and any queries will be generated in the EDC System to the Investigator or designee, enabling the errors to be addressed in parallel with Data

 GlaxoSmithKline	Document Name	Clinical Protocol 204930		
	Type	Version	Document Identifier	Effective Date
	eldo_clinical_doc	6.0; Most-Recent; Effective; CURRENT	090032d580c189ed	12-Sep-2016 05:12:55
	Reason For Issue	Auto Issue		

Management review. Monitor can also run reports and listings on the CRFs, to raise manual queries as needed for site clarification or correction

## 8.4. Processing Patient Reported Outcomes

Patient reported outcome (PRO) data are collected directly from the subject PRO measures e.g. diary cards, questionnaires etc, and entered into the sponsor's clinical data management system (DMS) by the study site representative. In instances where the PRO data is entered into the DMS by GSKCH, the PROs will be anonymised, and forwarded to GSKCH for entry, as agreed and documented ahead of the study starting. PROs that are source will be retained by the investigator and certified copies will be sent to GSKCH.

In order to protect the privacy of subjects, no Personally Identifiable Information (PII) (including the subject's name or initials or birth date) is to be recorded on all PRO's that will be forwarded to GSKCH.

In this study the DHEQ is a PRO. The DHEQ will be completed by the subjects as described in section 6.2.1. A member of the study site staff will enter the data into the CRF.

## 9. STATISTICAL CONSIDERATIONS AND DATA ANALYSES

### 9.1 Sample Size Determination

The sample size is based on DHEQ total Score, restrictions, adaptation, social impact, emotional impact and identity, from a previous study [GSKCH Study RH01897].

A sample size of 60 subjects will have at least 90% power to detect significant changes to week 24 for each of the DHEQ variables, with a significance level (alpha) of 0.05 using a two-sided one-sample t-test. No adjustments for multiple testing have been used. Approximately 75 eligible subjects will be allocated the study toothpaste in order to ensure that approximately 60 subjects complete the study. Sixty subjects will provide reasonable precision on estimates of DHEQ response and clinical DH assessments.

### 9.2. General Considerations

#### 9.2.1. Definition of Analysis Populations

The Safety population will consist of all subjects who received the study toothpaste.

 GlaxoSmithKline	Document Name	Clinical Protocol 204930		
	Type	Version	Document Identifier	Effective Date
	eldo_clinical_doc	6.0; Most-Recent; Effective; CURRENT	090032d580c189ed	12-Sep-2016 05:12:55
	Reason For Issue	Auto Issue		

The intention to treat (ITT) population will be defined as all subjects who received the study toothpaste and have at least one post- baseline DHEQ/clinical assessment.

The per-protocol (PP) population will be defined as all subjects who received the study toothpaste and have at least one post-baseline DHEQ/clinical efficacy assessment and have no protocol violations deemed to affect DHEQ/clinical efficacy assessments during the study. Further details will be provided in the statistical analysis plan (SAP).

Violations deemed to affect DHEQ/clinical efficacy assessments will be identified between the Biostatistician and Medical Director or designee pre analysis.

Analysis of the DHEQ and clinical efficacy measures (Schiff, LMS) will be performed on the ITT population. Analysis on the PP population will also be performed if there is more than 10% difference in the number of subjects between the ITT and PP populations.

### 9.2.2. Exclusion of Data from Analysis

Any of the following will be considered a protocol violation which may warrant exclusion of data or the subject from efficacy analysis:

- Violation of inclusion or exclusion criteria that are deemed to affect efficacy.
- Medical history which is deemed to affect efficacy.
- Use of prohibited treatment or medication before or during the study, which is felt to affect the assessment of efficacy.
- Treatment non-compliance
- Assessments outside the scheduled time windows
- Protocol deviations captured in CRF.
- Any other reason identified likely to affect efficacy

Protocol violations which warrant exclusion from efficacy analysis will be identified between the statistician and medical director or designee ahead of database lock.

### 9.2.3. Criteria for Evaluation

DHEQ measures captured in the study will be used evaluate changes in oral health related in quality of life over time. OST abnormalities, incidents and AEs reported in the study will be used for safety evaluations of the study treatments.

 GlaxoSmithKline	Document Name	Clinical Protocol 204930		
	Type	Version	Document Identifier	Effective Date
	eldo_clinical_doc	6.0; Most-Recent; Effective; CURRENT	090032d580c189ed	12-Sep-2016 05:12:55
	Reason For Issue	Auto Issue		

#### 9.2.4. Criteria for Assessing Efficacy

There are no formal success criteria in this study however it is expected that statistically significant changes from baseline will be observed for the DHEQ measures, in particular the Total score.

#### 9.2.5. Criteria for Assessing Tolerability

Safety will be assessed with respect to AEs, Incidents and OST abnormalities (oral tolerability).

#### 9.2.6. Handling of Dropouts and Missing Data

No data will be imputed in the case of dropouts or missing data.

#### 9.2.7. Other Issues

An interim analysis is not planned for this study.

### 9.3. Statistical Methods and Analytical Plan

More details of the proposed statistical analysis will be documented in the statistical analysis plan (SAP), which will be written following finalisation of the protocol and prior to study unblinding.

Selected raw data will be listed as defined in the SAP.

#### 9.3.1. Demographic and Baseline Characteristics

Descriptive statistics (number of subjects, mean, standard deviation, median, minimum and maximum for continuous variables, and frequency and percentage for categorical variables) will be provided for demographic and baseline data.

#### 9.3.2. Primary Analysis

The following DHEQ endpoints will be analysed:

- Section 1, questions 7, 8 and 9 as separate questions
- Total Score (34 item total from Section 2 questions 1 to 34)
- Domains:
  1. Restrictions (4 item total from Section 2 questions 1 to 4)
  2. Adaptation (12 item total from Section 2 questions 5 to 16)
  3. Social Impact (5 item total from Section 2 questions 17 to 21)
  4. Emotional Impact (8 item total from Section 2 questions 22 to 29)
  5. Identity (5 item total from Section 2 questions 30 to 34)
- Global Oral Health Rating (response to Section 2 question 35)

 GlaxoSmithKline	Document Name	Clinical Protocol 204930		
	Type	Version	Document Identifier	Effective Date
	eldo_clinical_doc	6.0; Most-Recent; Effective; CURRENT	090032d580c189ed	12-Sep-2016 05:12:55
	Reason For Issue	Auto Issue		

- Effect on Life Overall (4 item total from Section 2 questions 36 to 39)

**ABOVE DHEQ ENDPOINTS WILL BE ANALYSED USING MIXED EFFECT ANOVA WITH VISIT AND SITE AS FIXED EFFECT, SUBJECT AS RANDOM EFFECT. ADJUSTED MEANS WILL BE COMPUTED FOR EACH VISIT. USING THIS MODEL THE POST BASELINE VISITS WILL BE COMPARED TO THE BASELINE VISIT AND DIFFERENCE OF THEIR EFFECT WILL BE COMPUTED ALONG WITH P-VALUES AND 95% CONFIDENCE INTERVALS.**

**THE VISIT BY SITE INTERACTION WILL BE INVESTIGATED BY INCLUDING THE VISIT BY SITE INTERACTION TERM.**

**IF THE VISIT BY SITE INTERACTION TERM IS NOT SIGNIFICANT AT THE 10% LEVEL OF SIGNIFICANCE THEN THIS TERM WILL BE REMOVED FROM THE MODEL.**

**IF THE VISIT BY SITE INTERACTION TERM IS SIGNIFICANT AT 10% LEVEL OF SIGNIFICANCE THEN THE INTERACTION WILL BE INCLUDED IN THE MODEL AND ALL MODEL ESTIMATES (ADJUSTED MEANS, 95% CIs ANF P-VALUES) FOR WITHIN AND BETWEEN VISITS WILL BE REPORTED SEPARATELY FOR EACH SITE BASED ON THE RESULTS FROM VISIT BY SITE INTERACTION.**

Each of the DHEQ endpoints will be summarised by time point (Baseline, Week 4, 8, 12, 16, 20 and 24) ~~together with changes from baseline.~~

Standard summary measures ~~together with the changes from baseline,~~ 95% CIs and p-values ~~of changes from baseline~~ will be presented. A plot of means of raw scores over time (mean  $\pm$  standard errors) will also be presented for all measures.

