**PRESENTATIONS OF ENDPOINT SUMMARIES WILL ALSO BE PERFORMED BY SITE. NO INFERENCES WITHIN SITE WILL BE PROVIDED.**

~~P-values will be provided to test for non-zero changes from baseline in all measures.~~ Due to the exploratory nature of the study no correction of **FOR** multiple testing will be performed.

**THE ASSUMPTION OF NORMALITY AND HOMOGENEITY OF VARIANCE IN THE ANCOVA MODEL WILL BE INVESTIGATED. VIOLATION OF THESE ASSUMPTIONS MAY BE OVERCOME USING SUITABLE TRANSFORMATION OR PERFORMING A NON-PARAMETRIC TEST (E.G., THE WILCOXON SIGNED-RANK TEST).**

 GlaxoSmithKline	Document Name	Clinical Protocol 204930		
	Type	Version	Document Identifier	Effective Date
	eldo_clinical_doc	6.0; Most-Recent; Effective; CURRENT	090032d580c189ed	12-Sep-2016 05:12:55
	Reason For Issue	Auto Issue		

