## 5.2 Subgroups/Stratification

No subgroup or stratified analyses are planned.

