# 8 Efficacy Analysis

## 8.1 Primary Analysis

The null hypothesis for the primary analysis will be:

$H_0$ = There is no difference from baseline in DHEQ endpoints over time.

The alternative hypothesis will be:

$H_1$ = There is statistically significance difference from baseline in DHEQ endpoints over time.

The following DHEQ endpoints will be analysed:

- Section 1, questions 7, 8 and 9 as separate questions
- Total Score (34 item total from Section 2 questions 1 to 34)
- Domains:
  1. Restrictions (4 item total from Section 2 questions 1 to 4)
  2. Adaptation (12 item total from Section 2 questions 5 to 16)
  3. Social Impact (5 item total from Section 2 questions 17 to 21)
  4. Emotional Impact (8 item total from Section 2 questions 22 to 29)
  5. Identity (5 item total from Section 2 questions 30 to 34)
- Global Oral Health Rating (response to Section 2 question 35)
- Effect on Life Overall (4 item total from Section 2 questions 36 to 39)

 GlaxoSmithKline	Document Name	SAP 204930.doc		
	Type	Version	Document Identifier	Effective Date
	eldo_clinical_doc	1.0; CURRENT; Most-Recent; Effective	090032d580cb2f1e	10-Nov-2016 09:05:48
	Reason For Issue	Auto Issue		

Above DHEQ endpoints will be analysed using mixed effect ANOVA with Visit and site as fixed effect, subject as random effect. Adjusted Means will be computed for each visit. Using this model, the post baseline visit will be compared to the baseline visit and difference of their effect will be computed along with P-values and 95% confidence interval.

The visit by site interaction will be investigated by including the visit by site interaction term. If the visit by site interaction term is not significant at the 10% level of significance then this term will be removed from the model.

If the visit site interaction term is significant at 10% level of significance then the interaction will be included in the model and all model estimates (Adjusted Means, 95% CIs and P-values) for within and between visits will be reported separately for each site and based on results from visit by site interaction.

Each of the DHEQ endpoints will be summarised by time point (Baseline, Week 4, 8, 12, 16, 20 and 24).

Standard summary measures, 95% CIs and p- values will be presented. A plot of means of raw scores over time (mean  $\pm$  standard errors) will also be presented for all measures.

Due to the exploratory nature of the study no correction of multiple testing will be performed.

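### The protocol requires site-level p-values and 95% CIs after a 10% interaction test while saying no within-site inference will be given; the SAP keeps the tests and drops that statement, and tests selected this way do not hold 5%.

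*Protocol*

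**What the plan says.** Protocol 9.3.2 analyses each DHEQ endpoint "USING MIXED EFFECT ANOVA WITH VISIT AND SITE AS FIXED EFFECT, SUBJECT AS RANDOM EFFECT" and compares every post-baseline visit with baseline. A visit-by-site term is then tested at 10%. If it is not significant, it is dropped. If it is, all model estimates, including 95% CIs and p-values, "WILL BE REPORTED SEPARATELY FOR EACH SITE BASED ON THE RESULTS FROM VISIT BY SITE INTERACTION". A little further on, after providing for endpoint summaries by site, the section states "NO INFERENCES WITHIN SITE WILL BE PROVIDED". Protocol 9.3.3 applies the same interaction procedure to the Schiff and LMS scores and repeats the same restriction. Both instructions stand in current text.

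SAP 8.1 keeps the rule: estimates "will be reported separately for each site and based on results from visit by site interaction". SAP 8.2 does the same for the exploratory endpoints. Neither section carries over the protocol's restriction. SAP 5.2 adds "No subgroup or stratified analyses are planned". Protocol 9.3.2 and SAP 8.1 make no multiplicity correction.

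**The concern.** An analyst who follows the interaction rule produces within-site p-values that the protocol, read literally, says will not be provided. One who follows the restriction departs from the rule and from the SAP.

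There is also a statistical problem. Site-level tests appear only for endpoints where the data have already shown the sites diverging, and they are then read at the nominal 5% and 95%. An endpoint that trips the gate by chance tends to have one or both sites away from their true change. The report could then say that DHEQ changed significantly at one site and not at the other, with p-values and intervals that lack their stated properties. According to the amendment page, the second site was added because of recruitment problems. The sample size in Protocol 9.1 was set for the overall change, not for a conclusion at either site.

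**Working it through.** **Inputs**
- Level: two-sided 5% (Protocol 9.1, "with a significance level (alpha) of 0.05 using a two-sided one-sample t-test"; 95% CIs in 9.3.2).
- Subjects: N = 60 completers (Protocol 9.1).
- Visits: V = 7 (baseline and Weeks 4, 8, 12, 16, 20 and 24), so 6 interaction degrees of freedom and 6 baseline comparisons per site, 12 over two sites.
- Gate: 10% (Protocol 9.3.2).
- Site split: not given. The amendment page says only that a second site was opened for the rest of the recruitment. Assumed 30/30, with a range to 54/6.

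**The plan's own figure.** Protocol 9.1 states: "A sample size of 60 subjects will have at least 90% power to detect significant changes to week 24 for each of the DHEQ variables". No mean change or SD is given, so this cannot be reproduced. It can be inverted: by the noncentral t distribution, 90% power at n = 60 corresponds to a standardised change of about 0.425. The same change has about 61.5% power with 30 subjects and 34% with 15. The allocation is consistent with 20% dropout: 60 / 0.80 = 75.

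**Simulation.** Planned model, random subject intercept, complete data, no true change and no true interaction, 100,000 trials per split. With m(s,v) the site-by-visit mean of subject-centred data and MSE on (60 − 2) × (7 − 1) = 348 df:
- Gate: F = (n1·n2/N) × Σ over visits of [m(1,v) − m(2,v)]² / (6 × MSE), open if F > 1.79 (10% point on 6 and 348 df).
- Site test: t = [m(s,v) − m(s,0)] / √(2·MSE/n_s), significant if |t| > 1.967.

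The gate opens in about 10% of trials at every split. Given that it opens:

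| Split | Larger site | Smaller site | Average | Average / 5% |
|---|---|---|---|---|
| 30/30 | 12.9% | 12.6% | 12.8% | 2.6 |
| 40/20 | 9.9% | 15.2% | 12.5% | 2.5 |
| 45/15 | 8.6% | 16.7% | 12.6% | 2.5 |
| 50/10 | 7.4% | 18.5% | 12.9% | 2.6 |
| 54/6 | 6.6% | 19.2% | 12.9% | 2.6 |

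(At 30/30 the two columns differ only by simulation error.) The average is stable, but a single site ranges from 6.6/5 = 1.3 to 19.2/5 = 3.8 times nominal. At least one of the 12 site-by-visit tests for an endpoint is significant in about 75% to 77% of gated trials. With 75 subjects split 37/38 the per-test rate is 12.5% to 12.8%.

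**Other conditions, 30/30**
- Both sites share a real change: the site 95% CIs miss the true value in 12.7% of gated trials, so the fault does not depend on a null effect.
- Sites truly differ in change: gated non-coverage is 11.8% at a difference of 0.2 residual SD, 9.0% at 0.4, 6.3% at 0.6 and 5.0% at 0.8.
- No conditioning on the gate: each site test holds 5.0%. The chance that the gate opens and a given site test rejects is about 0.099 × 0.128 = 1.3%.
- Pooled visit-versus-baseline tests: 5.0% overall, and 5.0% among trials that do not pass the gate.
- If the true correlation were AR(1) at 0.7 to 0.85, the gated rate would be 19% to 21%, but the ungated level would already be 7% to 8%.

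**How often it arises.** SAP Appendix 3 lists 11 DHEQ measures. With no true site differences, 11 × 0.10 = 1.1 of them are expected to pass the gate.

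**The case against.** The restriction directly follows the sentence on by-site summaries. The amendment page shows that those summaries came with Amendment 2 and the mixed model with Amendment 3, so the restriction may have been meant for the summaries alone. The SAP output list fits that reading: the by-site tables (9.3.1.1, 9.3.1.2, 9.3.2.1 and 9.3.3.1) are summaries, and the statistical analyses sit in separate tables. SAP 5.2 adds little, because site is a model factor and the interaction test is a prespecified model check. This stands in part: a flat contradiction is not the only reading. But the protocol does not limit the restriction, and the SAP drops it without saying how site-level model output is to be treated. The selection problem remains on either reading.

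The study is also non-comparative and exploratory, with no formal success criteria, and the chance of a false site result for any one test is only 1.3%. This stands, and it limits the consequence. It does not repair the p-values and intervals that are actually shown, because those appear only after the gate.

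A reader might infer that the site tests run at 2.5 times their level in general, or equally at each site. The calculations do not support that. The multiple is conditional on a passed gate, assumes no true interaction and averages over the two sites. Nor is the pooled analysis shown to be faulty.

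**Conclusion.** The point holds in limited form. The protocol's two instructions need to be reconciled, and the SAP needs to agree with the result. As written, the rule produces site-level tests selected by the same data.

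The size of about 12.7% against a nominal 5% rests on the planned random-intercept model, complete data from 60 subjects, a passed gate and no true visit-by-site interaction. For one site the figure is about 7% to 19% over the assumed splits. It falls toward 5% as the true site difference grows. No formal decision depends on a site p-value, so the risk is a misleading site-specific statement in the report, not an error in the main conclusion.

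**What to change.** In Protocol 9.3.2 and 9.3.3 and SAP 8.1 and 8.2, replace the site-level part of the interaction rule with wording to this effect:

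- The visit-by-site interaction p-value will be reported for each endpoint.
- If it is below 10%, adjusted means and visit-minus-baseline differences will be shown by site as descriptive information only. No site p-values will be given and no conclusion will be drawn for a single site.
- Standard errors will be shown in place of site 95% CIs; or any site CIs will be labelled as descriptive and not adjusted for the interaction test.

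Removing the p-values alone is not enough, because gated CIs have the same coverage fault and a reader can see whether they exclude zero. Carry the restriction "NO INFERENCES WITHIN SITE WILL BE PROVIDED" into SAP 8.1 and 8.2, so that the documents agree whichever scope was first intended.

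The cost is wording. The SAP lists no by-site inferential table, and the analysis templates shown carry no by-site p-value columns, so no listed output is lost. The small downside is that a real site difference would be described without a site-specific p-value; the interaction p-value would still show it.
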